8.4 Sample size and power

The sample size of two times 500 patients is a trade-off between precision and exposing an excessively high number of patients to potentially more toxic treatment. Power has not been taken into account, but if the results are favourable large scale cluster-randomized study will be designed to bring definitive proof.

The registered incidence of clinically apparent hepatitis from any cause during TB treatment is 1.5% for the study population. With the proposed sample size, an increase by at least 2% compared to the control arm will attain statistical significance ($p=0.047$).

With the standard (=control) regimens and definitions, about 2% failures and 2% relapses are currently notified by the DF project, but only 50% of those are culture-positive, and about half of the culture positive failures and relapses are rifampicin-resistant. Overall cure rate (new and retreatment cases together) is close to 90%, with 4% default and 4% deaths. Based on the data from 2010 about 20 cases with rifampicin resistance may be enrolled, 10 in each arm. We estimate that the more effective study regimen plus early detection of serious drug resistance rolled over to MDR-TB

treatment will prevent drug resistant failure and relapse, reduce rifampicin susceptible relapse to an estimated two third, and reduce death and default because of unrecognized rifampicin resistance to 80% of the control arm. This total estimated reduction of unfavourable outcome from 10% to 7% remains non-significant with the targeted enrolment of two times 500 cases. With 80% power and 95% confidence level, 2 x 1421 patients would have to be enrolled, which is not feasible and also difficult to justify. However, a slightly larger reduction of unfavourable outcome from 10% to 6.5% comparing two arms of 500 cases each would already result in a significant p-value. Additional evidence will be obtained studying *rpoB* mutations, initially (all smear-positives) and at time of failure or relapse (only in the few such cases expected). Absence of low-level resistance mutations only among patients with unfavourable outcome on the high-dose arm, while they were present among new cases in both arms, will be interpreted as additional evidence of effectiveness of the increased dosing.

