3.1 Primary endpoints

The primary efficacy endpoint is the incidence of adverse treatment outcomes. Following the WHO guidelines from 2010¹⁸, as currently in use in the NTP in Bangladesh, outcomes are defined as follows:

- Cured: A patient whose smear or culture was positive at the beginning of treatment but who was smear- or culture-negative in the last month of treatment and on at least one previous occasion.
- Completed: A patient who completed treatment but who does not have a negative sputum smear or culture result in the last month of treatment and on at least one previous occasion.

- Relapse: Cured previously from TB or completed treatment for TB and now having bacteriologically positive sputum for TB (at 12 months follow-up or at an earlier time point)
- Default: The patient whose treatment was interrupted for ≥ 2 consecutive months or more.
- Failure: Sputum positive for TB at 5 months or later during treatment. In line with current WHO recommendations, patients detected with MDR-TB or rifampicin resistance before this or another outcome applies and switched to the MDR-TB regimen will be excluded from the outcome analysis.¹⁸ Failure will also be declared if the regimen has to be changed for at least 2 drugs due to adverse events.
- Death: All-cause mortality between case registration and end of TB treatment (related or not to TB or TB treatment)
- Transfer out: A TB patient who transferred out to another recording and reporting unit and whose treatment outcome is unknown.

Analyses will be performed using the NTP smear-based recurrence (failure, relapse) definitions, but as a secondary approach culture-based definitions will be used.

Safety:

The primary safety endpoint will be the occurrence of any of the following:

- Serious Adverse Events
- Grade 3-4 Liver Toxicity following NIH common toxicity criteria (CTC), including transaminase increases to $>5-20$ ULN (grade 3), or > 20 ULN (grade 4)

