### 8.2.2. *Grade 3-4 Liver Toxicity*

The total number of patients with grade 3, grade 4 and grade 3-4 liver toxicity up to 12 months after treatment stop will be presented. Statistical tests of association, using logistic regression, adjusted for hospital and stratum (new/ retreatment case), between treatment and liver toxicity will be performed.

Due to the multiplicity of tests performed, the statistical tests of association between treatment and safety outcomes will not be interpreted as definite proof of more or less harm of any of the treatment but will be used as a screening tool. The use of a statistical tests will allow the exclusion of any observed difference which may be due to chance.

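### Section 8.4 promises significance for a 2-point rise in hepatitis that occurs only about half the time, and gives no figure for the primary safety endpoint

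*Protocol*

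**What the plan says.** Protocol 8.4 sets the size without a power target: "The sample size of two times 500 patients is a trade-off between precision and exposing an excessively high number of patients", and "Power has not been taken into account". It then makes one quantitative statement about safety. The base rate is given as "The registered incidence of clinically apparent hepatitis from any cause during TB treatment is 1.5% for the study population", and for 500 per arm "an increase by at least 2% compared to the control arm will attain statistical significance", with p=0.047. No test is named.

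Protocol 3.1 defines a different endpoint. "The primary safety endpoint will be the occurrence of any of the following": serious adverse events, or grade 3-4 liver toxicity. SAP 4.2 repeats this composite. Protocol 7.1 counts death and in-patient hospitalisation among the outcomes that make an event serious.

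The planned analysis is a logistic model. Protocol 8.3.3 applies the primary efficacy method to the safety endpoint, and SAP 8.2.2 specifies, for liver toxicity, "Statistical tests of association, using logistic regression, adjusted for hospital and stratum". SAP 8.2.1 does the same for serious adverse events.

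Protocol 2.1, Protocol 8 and SAP 1 all make the absence of excess toxicity one of the grounds for going on to the cluster-randomised trial.

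**The concern.** The sentence in 8.4 turns a property of an observed table into a statement about what the trial will show. A reader takes from it that a 2-point rise in toxicity could not go unnoticed with 500 per arm. It also uses an endpoint that is narrower and rarer than the one on which safety will be judged.

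The go/no-go criterion is where this matters. SAP 8.2.2 also says that the safety tests will let differences that may be due to chance be set aside. A real 2-point excess could therefore be non-significant, and the wording of 8.4 would encourage reading that result as reassurance.

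**Working it through.** **Inputs.** From Protocol 8.4: 500 per arm, 1.5% hepatitis, a 2-point increase and p=0.047. The two-sided 5% level is inferred, because 0.047 reproduces two-sided. The control rate of the primary safety endpoint is not in the documents and is treated below as an assumption.

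**1. Reproducing p=0.047.** 1.5% of 500 is 7.5, so take 8 v 18. The pooled rate is 26/1000 = 0.026.

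z = 0.02 / √(0.026 × 0.974 × 2/500) = 0.02 / 0.01006 = 1.987, so p = 0.0469.

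This is the plan's figure: a Pearson chi-square without continuity correction.

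**2. How far it depends on the control count.** Keep the observed excess at exactly 10 cases (2 points):

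| Control v intervention | Chi-square p |
|---|---|
| 7 v 17 | 0.039 |
| 8 v 18 | 0.047 |
| 9 v 19 | 0.055 |
| 10 v 20 | 0.064 |

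With a true control rate of 1.5%, the binomial chance of 9 or more control cases in 500 is about 34%.

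**3. How far it depends on the test.** For 8 v 18:

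- Unadjusted logistic, Wald: log odds ratio 0.831, standard error 0.430, z = 1.935, p = 0.053.
- Unadjusted logistic, likelihood ratio: p = 0.044.
- Chi-square with continuity correction: p = 0.074.
- Fisher's exact test: p = 0.072.

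The plan does not say whether Wald or likelihood-ratio p-values will be reported, and the p-value adjusted for hospital and stratum cannot be computed from the documents. The efficacy figure of 2 × 1421 in the same section is approached only with a continuity correction (1422 per arm, against 1356 without), so 8.4 appears to mix conventions.

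**4. Chance of significance if the true rates are 1.5% and 3.5%.** With mean rate p̄ = 0.025:

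Power = Φ{ [Δ√n − 1.96√(2p̄(1−p̄))] / √(p₁(1−p₁) + p₂(1−p₂)) }

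= Φ{ [0.4472 − 0.4327] / 0.2203 } = Φ(0.066) = 53%.

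Exact enumeration of the two binomials gives 54% for the chi-square and 51% for the unadjusted Wald test.

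**5. The primary safety endpoint.** One route to a control rate is to add programme mortality in 8.4 ("with 4% default and 4% deaths") to the 1.5% hepatitis without overlap, which gives 5.5%. That is an assumption, so a range is shown. The half-width is 1.96√(2p(1−p)/500), with equal rates in the two arms. Power is by exact enumeration (chi-square). The last column is the smallest excess, to a tenth of a point, at which that exact power reaches 80%.

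| Assumed control rate | 95% CI half-width (points) | Power for a true 2-point excess | True excess for 80% power (points) |
|---|---|---|---|
| 2% | 1.7 | 46% | 3.3 |
| 4% | 2.4 | 30% | 4.3 |
| 5.5% | 2.8 | 25% | 4.8 |
| 8% | 3.4 | 20% | 5.5 |

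If the arms truly differ by 2 points the interval is slightly wider: at 5.5% v 7.5% the half-width is 1.96√((0.051975 + 0.069375)/500) = 3.05 points.

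An observed 2-point excess near 5.5% (27 v 37) gives chi-square p = 0.196, so the statement about hepatitis does not carry over.

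**The case against.** The plan is candid about its limits. Protocol 8.4 says that power was set aside. Protocol 8.1 puts the focus on estimates and confidence intervals and asks that p-values be read with care. SAP 8.2.2 calls the safety tests a screening tool. The sentence speaks of hepatitis and does not claim to size the composite, and its p-value is computed correctly. All of that stands, and it makes the consequence smaller. It does not make the promise of significance true, and a pilot built on estimation should state its expected precision.

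A reader might infer four stronger things that the documents do not support:

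- *Only the single table 8 v 18 is significant.* Only the value 0.047 belongs to that table. A 10-case excess is also significant by chi-square at every lower control count, and 7 is as fair a rounding of 7.5 as 8.
- *The planned model overturns the claim.* The Wald and likelihood-ratio p-values fall on opposite sides of 0.05, so the result is borderline, not reversed.
- *The composite rate is at least 4%.* The 4% is programme mortality. Protocol 4.2 excludes patients who need hospitalisation, have active liver disease, or have known HIV or hepatitis B or C. A lower rate is possible, which is why 2% is in the table.
- *Power is 25%.* That holds only for an assumed 5.5%.

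Nor do the documents define absence of excess toxicity as p>0.05, or show that the DSMB relies on 8.4.

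**Conclusion.** The concern holds as a matter of wording and endpoint match; there is no arithmetic error. The p-value of 0.047 is right for 8 v 18 by an uncorrected chi-square. As a statement of what 500 per arm will deliver it is wrong: for a true rise from 1.5% to 3.5%, the chance of significance is about one half. No control rate, precision or detectable difference is given for the primary safety endpoint. Over assumed control rates of 2% to 8%, a true 2-point excess would be significant in about 46% to 20% of trials, so under that assumption it would more often be missed than found. The hepatitis result rests on the plan's own 1.5%. The composite results rest on assumed rates, and all power figures here are for unadjusted tests.

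**What to change.** Replace the significance sentence in Protocol 8.4 with text such as:

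> For clinically apparent hepatitis (1.5%), an observed 2-point excess lies at the edge of significance; if the true excess is 2 points, the chance of p<0.05 is about 50%. The control rate of the primary safety endpoint is not known. For assumed rates of 2%, 4%, 5.5% and 8%, 500 per arm gives a 95% CI half-width for the difference (equal rates) of about 1.7, 2.4, 2.8 and 3.4 points, and power for a true 2-point excess of about 46%, 30%, 25% and 20%; 80% power needs a true excess of about 3.3, 4.3, 4.8 and 5.5 points. A non-significant difference is therefore not evidence that excess toxicity is absent; the confidence interval will be used.

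If the programme has a better estimate of the composite rate, it should replace the assumed range. The cost is one paragraph and a less favourable stated figure. Sample size, endpoints and conduct do not change.

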1.2 Rationale

Low-level resistance to rifampicin is not rare, and is easily missed by conventional DST. About 15% of all rifampicin resistance in retreatment cases is low level.^{3, 4} However, an as yet unpublished survey among our target study population suggests that this proportion may even reach 50% in new cases. Each of these mutations is rare, but a large variety exists. They are detected by absent or reduced signals with wildtype probes by molecular test formats, such as lineprobe assays and the Xpert MTB/RIF assay. This can cause substantial confusion in the interpretation and decision making when conventional DST suggests (false) rifampicin susceptibility. This is particularly problematic in the MGIT system, in which the standard 12 day read-out misses rifampicin resistance in strains with those mutations, while the control tube already meets acceptance criteria for growth. For the same reason the significance of these low-level resistance mutations remains disputed. There is nevertheless evidence that cases caused by such strains can cause outbreaks of MDR and even XDR-TB. Such strains also lead to a high frequency of adverse outcomes in individual cases, comparable to those of the high-level resistance mutations (63% failure/relapse of standard primo-treatment in our reference 2). The MIC of most low-level mutations is around the peak level in serum and tissues achieved with the standard dose of rifampicin. This could explain why more MDR with these mutations seem to be curable with the unmodified Cat. 1 or 2, but often resulting in subsequent relapse.

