4.3 Sample size

The sample size selected is 1000 patients (500 randomized to intervention, 500 to control). The study will be conducted in eight DF Bangladesh outpatient clinics with an LED TB fluorescence microscopy laboratory that register about 2000 TB cases per year of which 65% are smear-positive pulmonary TB (new or retreatment). Enrolment will target 1000 randomised smear-positive pulmonary TB patients. Given an expected 5% refusal rate, it is expected that recruitment will require 9-10 months.

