#### Testing

In addition to standard monitoring (as described above for the control arm), patients in the intervention arm will have sputum tested by auramine and FDA smear after the first and again after the second week of intensive phase treatment. Management decisions will be made after 2 weeks of intensive phase, based on remaining numbers and decline of AFB on FDA staining, but not based on continuing fever. Those with min. 1 log decline in the number of AFB, or who are already negative, would continue the unaltered regimen. Those not meeting these criteria would be referred for rapid DST by slide DST and/or Xpert MTB/RIF, depending on ease of referral.

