#### 4.2. Efficacy study endpoints

##### *Primary endpoint*

The primary efficacy endpoint is the incidence of adverse treatment outcomes. Following the WHO guidelines from 2010, as currently in use in the NTP in Bangladesh, an adverse treatment outcome is defined as any occurrence of the following:

- Relapse: Cured previously from TB or completed treatment for TB and now having bacteriologically positive sputum for TB (at 12 months follow-up or at an earlier time point)
- Default: The patient whose treatment was interrupted for 2 consecutive months or more.

- Failure: Sputum positive for TB at 5 months or later during treatment. Failure will also be declared if the regimen has to be changed for at least 2 drugs due to adverse events.
- Death: All-cause mortality between case registration and end of TB treatment (related or not to TB or TB treatment)

Patients who are transferred out will be excluded from the outcome analysis.

In line with current WHO recommendations, patients detected with MDR-TB or rifampicin resistance before any outcome applies and switched to the MDR-TB regimen will be excluded from the outcome analysis.

Analyses will be performed using the NTP smear-based recurrence (failure, relapse) definitions, but as a secondary approach culture-based definitions will be used. In each analysis, if a patient has two events for the analysis of interest, the first endpoint will be taken into account, except for cured/completed followed by relapse which is considered as relapse.

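### Absence of low-level rpoB mutations among unfavourable outcomes on high dose cannot separate a dose effect from chance or from the arm-specific week-2 screening

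*Protocol*

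**What the plan says.** Protocol 8.4 (Sample size and power) sets out a pattern that the team would read as supporting the higher dose: "Absence of low-level resistance mutations only among patients with unfavourable outcome on the high-dose arm", "while they were present among new cases in both arms". Such a finding "will be interpreted as additional evidence of effectiveness of the increased dosing". The sentence gives no minimum number of carriers and no probability of the pattern arising by chance. It does not say clearly whether control-arm outcomes must show the mutations.

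Other parts of the plan bear on it:

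- **Expected numbers.** Protocol 8.4: "Based on the data from 2010 about 20 cases with rifampicin resistance may be enrolled, 10 in each arm". Protocol 4.3: "500 randomized to intervention, 500 to control".
- **Risk on standard dose.** Protocol 1.2 reports for low-level strains "63% failure/relapse of standard primo-treatment".
- **Screening.** SAP 2.1 (Testing): "patients in the intervention arm will have sputum tested by auramine and FDA smear after the first and again after the second week". At week 2 the intervention arm is referred for rapid DST on insufficient FDA decline, the control arm on persisting fever (Protocol 2.1 and 5.3).
- **Exclusion.** SAP 4.2: "patients detected with MDR-TB or rifampicin resistance before any outcome applies and switched to the MDR-TB regimen will be excluded from the outcome analysis". Protocol 3.1 has the same rule.
- **Related analyses.** Protocol 8.3.4 objective 1 compares adverse outcomes by arm within baseline mutation groups. SAP 7.1 tests the arm-by-mutation interaction in the main model. SAP 7.2 compares by arm how much initial resistance was switched early and how much was neither switched nor cured.

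**The concern.** The inference starts from patients who did badly and asks whether carriers are among them. With very few carriers, none may appear there by luck. Carriers can also disappear for a reason unrelated to dose: if the week-2 screen finds them, they are switched and are no longer counted as unfavourable. The two arms use different screens, so this removal can differ by arm. Protocol 8.4 itself attributes the hoped-for benefit to the regimen together with early detection, yet the sentence credits the dose alone.

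At stake is a screening effect, or a chance result, being reported as evidence that doubling the dose overcomes low-level resistance. The go/no-go considerations in Protocol 2.1 and section 8 also mention possible benefit for low-resistance mutations, so such a report could colour the decision on the larger trial.

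**Working it through.** **1. The plan's figure.** The 2010 survey found 2% resistance in new cases (Protocol 1.1, reported as MDR-TB). 0.02 × 1000 = 20, or 10 per arm. This reproduces the figure in Protocol 8.4. The plan states no error rate for the inference.

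**2. Carriers per arm (m).** Protocol 1.2 puts the low-level share of rifampicin resistance at about 15% in retreatment cases and possibly as high as 50% in new cases.
- 10 × 0.15 = 1.5
- 10 × 0.50 = 5

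**3. Risk with no dose effect.** 63% failure or relapse. If a share s of carriers is switched and leaves the analysis, each carrier contributes a counted bad outcome with probability q = 0.63 × (1 − s). The documents do not give s. I assume s = 0 (q = 0.63) and s = 0.5 (q = 0.315).

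**4. No carrier among high-dose bad outcomes, given at least one carrier in that arm.** With Poisson counts,

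P = [exp(−mq) − exp(−m)] / [1 − exp(−m)].

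| m | s | Calculation | P |
|---|---|---|---|
| 1.5 | 0 | (0.3887 − 0.2231)/0.7769 | 21.3% |
| 5 | 0 | (0.0429 − 0.0067)/0.9933 | 3.6% |
| 1.5 | 0.5 | (0.6234 − 0.2231)/0.7769 | 51.5% |
| 5 | 0.5 | (0.2070 − 0.0067)/0.9933 | 20.2% |

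A binomial model with 10 resistant cases per arm gives 2.2% (m = 5, s = 0) to 52.2% (m = 1.5, s = 0.5).

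**5. Carriers required in both arms.** The sentence requires this, so the joint chance is P × [1 − exp(−m)]².
- s = 0: 12.9% (m = 1.5) and 3.6% (m = 5)
- s = 0.5: 31.1% (m = 1.5) and 19.9% (m = 5)

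These are values at the two ends of m. The joint chance is not monotone: at m = 2 and s = 0.5 it is (0.5326 − 0.1353) × (1 − 0.1353) = 34%.

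**6. Reading *only* as a contrast with control outcomes.** Require also at least one carrier among control unfavourable outcomes, so multiply [exp(−mq) − exp(−m)] by the chance of that. At m = 1.5 and m = 5 respectively:
- nobody switched: 0.1656 × 0.6113 = 10.1%, and 0.0361 × 0.9571 = 3.5%
- half switched in the intervention arm only: 0.4003 × 0.6113 = 24.5%, and 0.2003 × 0.9571 = 19.2%
- half switched in both arms: 0.4003 × 0.3766 = 15.1%, and 0.2003 × 0.7930 = 15.9%

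Intermediate m again gives somewhat higher values, for example about 30% at m = 2.5 with half switched in the intervention arm only.

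**7. Sensitivity.** Adding 8 points to the risk for death and default (4% each in Protocol 8.4; adding them is my assumption) moves the range in step 4 from 3.6%–51.5% to about 2%–47%. At m = 5, switching 75% or 90% of carriers gives 45% or 73%.

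**The case against.** A good deal can be said for the plan.

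- The sentence speaks of new cases, while the 15% share is stated for retreatment cases. Retreatment suspects found resistant before treatment are not eligible (Protocol 4.2 and 5.3), so resistant participants should be mainly new. At the 50% share the chance is 3.6% with no switching, inside a conventional 5%. This stands, with the caution that Protocol 1.2 gives 50% as an upper value.
- Switching half the carriers is an assumption. Protocol 1.2 calls the screening cut-off not yet settled, and there is reason to expect a lower yield for low-level strains: isoniazid alone gives about a 1-log kill in two days, and these patients often seem cured and relapse later. This stands.
- The word *only* may imply a contrast with control outcomes. The wording is ambiguous, and that reading lowers the figures (step 6).
- Analyses with a proper denominator are already planned. This stands in part. A reader might infer that the plan never looks at all carriers; Protocol 8.3.4 and SAP 7.1 and 7.2 show otherwise. But SAP 7.1 uses the main model, which drops switched patients, and SAP 7.2 accounts for switching but is not split by mutation level. Neither withdraws the sentence in 8.4.
- A reader might infer a formal rule for declaring efficacy or for go/no-go. The documents do not support that. The sentence offers additional evidence in a pilot, Protocol 8.1 puts estimation ahead of testing, the SAP does not repeat the sentence, and the go/no-go text does not cite it.

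**Conclusion.** The inference is unsound as written. Its main flaw does not depend on any assumed number: screening differs by arm and switched carriers leave the outcome analysis, so absence among bad outcomes cannot be credited to dose alone.

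The size does depend on assumptions. Given a carrier in the high-dose arm, the chance of the pattern with no dose effect is about 4% to 21% with no switching and about 20% to 52% if half are switched. Requiring carriers in both arms gives about 4% to 31% at the same inputs, and less under the contrast reading. All of this takes 63% as the risk without a dose effect and Poisson counts with mean 1.5 to 5.

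A reader might take away a false-positive rate of 52%. The documents do not support that as a single figure: it needs both the retreatment-case share and an assumed 50% switch rate. Nor do they show which screen finds more low-level carriers, so the direction of the screening effect is unknown.

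**What to change.** Delete the inference from absence alone in Protocol 8.4. In its place there, and in SAP 7.1 and 7.2, specify the following:

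- For all randomised patients with a low-level mutation in the baseline rpoB sequence, report by arm three separate categories: cured on the allocated regimen, unfavourable outcome, and switched to the MDR regimen.
- Give exact 95% confidence intervals, with switched patients kept in the denominator.
- State that any difference between arms reflects dose and screening together.

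The categories should stay separate. A single endpoint of cure without a switch would count each switch against the arm whose screen finds more carriers, so it would be confounded too.

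This is a change of wording. Protocol 5.4 already sends pre-treatment specimens from all enrolled patients for rpoB sequencing, so no new data are needed. The downside is a less favourable statement of evidence, and an imprecise one with so few carriers.
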